## 7 INVESTIGATIONS SCHEDULE

In cases where a patient has investigations at a different hospital, for example weekly blood samples, scans and other investigations as appropriate, then it is the Investigator's responsibility to ensure he/she receives and reviews the reported results. These results must be available for source data verification. Laboratory reference ranges, including effective dates, and evidence of laboratory accreditation must be obtained from all laboratories used. For scan results, the original images and reports must be available for comparison to any scan performed at the investigator site and be in a format that is suitable for comparison. For all other investigations, apart from the results, any supporting data must also be made available for source data verification or review.

The Investigator or delegate must inform the Sponsor of any changes to their laboratory normal ranges or to any laboratory accreditation and provide any new documentation.

### 7.1 Pre-treatment evaluations

Details of all evaluations/investigations for enrolled patients, including relevant dates, required by the protocol must be recorded in the medical records.

At the first visit to the participating clinical site and identified as a potential patient by the clinical team, patients will be asked to consent to a blood sample for HLA typing analysis. As HLA analysis and confirmed type is an inclusion criterion, patients who do not consent to this analysis will be unable to enter the trial. It will be clear in the accompanying informed consent document (ICD) that agreement to the HLA analysis does not mean that entry into the main trial is confirmed but that it is one of several screening procedures. If the patient consents, the blood sample will be taken at that visit.

#### 7.1.1 Obtaining written informed consent

Written informed consent must be obtained from the patient before any protocol-specific procedures are carried out.

##### 7.1.1.1 Pre-screening: HLA testing

All potential patients will be asked to consent to HLA testing prior to entering main trial screening. The result of the HLA testing must be known before the patient is introduced to the main patient information sheet. A three mL blood sample will be taken for central lab analysis. Only HLA A\*02:01 positive patients will be asked for consent to enter trial screening for the main trial.

The result of HLA testing must be known and the patient must have signed the separate main trial consent before the patient enters the main trial screening stage.

##### 7.1.1.2 Main trial consent and screening

#### HLA A\*02:01 positive patients:

The patient must be given adequate time to think about their commitment to the trial and whether they would agree to being enrolled onto the trial to receive trial treatment. If consent was taken more than 28 days prior to the first AST-VAC2 vaccination then it is the responsibility of the Investigator to determine if further consent should be taken. If there has been a change to the ICD, then the patient must be made aware of the changes made and reasons for the change(s) and consent must be taken again.

#### For all patients:

Only the Principal Investigator (PI) and those Sub-Investigator(s) with delegated responsibility by the PI, and who have signed the Delegation Log, are permitted to obtain informed consent from patients and sign the consent form. All signatures must be obtained before the occurrence of any medical intervention required by the protocol (ICH GCP 4.8.8 and 8.3.1.2). The patient should sign and date the consent form in the presence of the Investigator, followed by the Investigator signature. The date of the

## CONFIDENTIAL

signatures of both the patient and the PI/Sub-Investigator obtaining informed consent should be the same.

The PI or the Sub-Investigator must inform the patient about the background to their disease and the normal management of their disease alongside information about the AST-VAC2 trial. The investigator must also ensure that the patient is aware of the following points:

- That AST-VAC2 is new and that the exact degree of activity is at present unknown, but that treating him/her will contribute to further knowledge.
- Any known toxicity of AST-VAC2 and the possibility of experiencing side-effects.
- The potential dangers of becoming pregnant (or the patient's partner becoming pregnant) and he/she has been given information about appropriate medically approved contraception (refer to Section 9.7).
- That he/she may refuse treatment either before or at any time during the trial and that refusal to participate will involve no penalty or loss of benefits to which they are otherwise entitled.
- Whom to contact for answers to pertinent questions about the research and their rights, and also who to contact in the event of a research-related injury.
- That long-term follow-up is required because it is an advanced therapy investigational medicinal product (ATIMP). Consent for long term follow up will be requested at the time of trial enrolment.

A copy of the ICD for the main trial must be given to the patient to keep and the original ICD must be filed in the Investigator Trial File (ITF) (unless otherwise agreed that the original document will be filed in the medical records and a copy kept in the ITF).

### 7.1.2 Evaluations within 28 days prior to administration of AST-VAC2 (Baseline) (Day -28 to Pre-vaccination on Day 1)

The following must be performed/obtained **within 28 days before** the patient receives their first AST-VAC2 vaccination (and post confirmation that the patient is HLA A\*02:01 positive):

Existing results such as radiological measurements may be used even where these investigations were performed prior to the patient's provision of informed consent for the trial, if they were performed within the required time window.

- Written informed consent (may be taken more than 28 days before, see [Section 7.1.1.2](#)).
- Demographic details.
- Medical history including prior diagnosis (histologically or cytologically proven lung cancer), prior treatment, concomitant conditions/diseases and baseline signs and symptoms, concomitant treatment.
- Radiological disease assessments: Radiological measurements (computerised tomography (CT) scan, to cover chest, thorax, abdomen, pelvis, liver) and/or magnetic resonance imaging (MRI) – must be performed **within four weeks before** the patient receives the first dose of AST-VAC2. Tumour measurements must be reported according to Immune Response Related Criteria (irRC) – [Appendix 3](#).

- 

Note that all AEs, including Serious AEs, must be monitored and recorded in the eCRF from the time the patient consents to any protocol-specific procedure, including consent for HLA typing (see [Section 9.3](#)) for further details). If the patient is administered a COVID-19 vaccine during the trial screening period, this should be documented in the eCRF as a concomitant medication and any AEs should be assessed for causality to the COVID-19 vaccination.

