### 9.3.2 Patients who consent to HLA screening

AEs and SAEs related to the HLA test procedure should be reported from the time of HLA test consent to the time of consent to the main trial. Thereafter, should the patient consent to the main trial, reporting requirements as per [Section 9.3.4](#).

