### 9.3.3 Eligible patients

For eligible patients, SAE and AE collection and monitoring will commence at the time the patient gives their written consent to participate in the trial by signing the main trial consent form and will continue until 30 days after the last vaccination (administration of IMP). From this time point until the patient withdraws, dies or completes the trial, new or ongoing AST-VAC2-related AEs will be collected (regardless of whether the patient goes on to other anti-cancer therapies).

Should an Investigator become aware of any AST-VAC2 -related SAEs after the patient has completed the protocol-mandated follow-up period (as specified above), these must also be reported to the Sponsor within the expedited timelines in Section 9.4.

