### 13.4 Safety

Safety data will be collected from the date of written consent until patients have completed their required follow up period. Safety variables will be summarised by descriptive statistics. Laboratory variables will be described using the NCI CTCAE Version 4.02 and the protocol specific grading system for ISRs.

Adverse events will be reported as tables of frequency of AEs by body system and by worse severity grade observed. Tables should indicate related and unrelated events.

Deaths reported within 30 days of the last vaccination and SAEs will be described separately.

A safety review committee, consisting of all investigators and representatives of the Sponsor, will review emerging safety data on an ongoing basis, with particular reference to ensuring that patients are able complete the vaccination schedule without AST-VAC2 toxicity-related delays. Should the committee

have significant concerns about toxicity seen during the trial they will have the authority to suspend or terminate the trial and/or make recommendations to the Sponsor to modify vaccination administration.

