5.14.4 Interim analysis

An interim analysis will be conducted once all patients administered AST-VAC2 have withdrawn, died or completed their 2-year follow-up visit for survival. Once this condition is met, a data cut-off will be established. All patient visits occurring on or before this date will be analysed and summarised in the clinical study report including safety data to date and assessment of OS at 2 years.

Any data collected after this date will be summarised in a supplemental report produced for the final analysis to satisfy the safety reporting requirements for AST-VAC2 as an advanced therapy investigational medicinal product (ATIMP).

The relevant data will be uploaded to ClinicalTrials.gov after the CSR is approved.

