7. PRESENTATION OF RESULTS IN CLINICALTRIALS.GOV INCLUDING ADDITIONAL TABLES

The following information will be used for presentation and upload of trial data on ClinicalTrials.gov. The data presented will be consistent with the final CSR but will be tabulated in a format that fits with the ClinicalTrials.gov requirements¹.

The tables programmed for ClinicalTrials.gov will **not** form part of the Clinical Study Report (CSR).

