7.5 Outcome Measures

Primary and secondary endpoints will be reported on the ClinicalTrials.gov website as outcome measures as follows. Results will be reported for all Primary and Secondary Endpoints.

Primary Objectives	Endpoints	Outcome Measures
To assess the safety and tolerability of AST-VAC2	Determining the frequency and causality of each adverse event to AST-VAC2 and grading severity according to the NCI CTCAE Version 4.2 or protocol specific grading system for injection site reactions (ISRs).	
Measure Title: Frequency and Causality of Serious Adverse Events (SAEs), Non-Serious Adverse Events (NSAEs) and Grade ≥ 3 Adverse Events (AEs) to AST-VAC2
 
Measure Description: Number of SAEs, NSAEs and Grade ≥ 3 AEs overall and number of SAEs, NSAEs and Grade ≥ 3 AEs related to AST-VAC2. AEs categorised according to Medical Dictionary for Regulatory Activities version (v) X and graded for severity according to National Cancer Institute Common Terminology Criteria for Adverse Events v4.02 or protocol specific grading system for injection site reactions (ISRs; Section 9.8 of protocol). AEs assessed by the reporting study doctors for a causal relationship to AST-VAC2. Related are those AEs with a causality of possible, probable or highly probable.
 
Time Frame: From the time of informed consent up to 2 years from the first dose of AST-VAC2, a median (range) of XX days (XX-XX).
 
Measure Type: Number
 
Measure of dispersion/precision: Not applicable
 <hr/> 
Measure Title: Number of Participants Experiencing ISRs by Grade
 
Measure Description: Number of participants experiencing ISRs Grade 1 to 4 according to protocol-specific grading of ISRs (Section 9.8 of protocol).
 
Time Frame: From the time of informed consent up to 2 years from the first dose of AST-VAC2, a median (range) of XX days (XX-XX).
 
Measure Type: Count of participants
 
Measure of dispersion/precision: Not applicable

Secondary Objectives	Endpoints	Outcome Measures

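### The posted primary AE counts start at consent with no treatment-emergent restriction, so pre-vaccination events enter them, and the protocol disagrees with itself on which consent starts AE collection

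*Protocol*

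**What the plan says.** **Start of collection.** Protocol 7.1.2 has all AEs, serious ones included, recorded in the eCRF "from the time the patient consents to any protocol-specific procedure, including consent for HLA typing", and points to Section 9.3 for detail. Section 9.3 is narrower. Under 9.3.2, "AEs and SAEs related to the HLA test procedure should be reported from the time of HLA test consent", and this lasts until main consent. Under 9.3.3, collection for eligible patients "will commence at the time the patient gives their written consent to participate in the trial by signing the main trial consent form". Protocol 13.4 does not settle the matter: "Safety data will be collected from the date of written consent until patients have completed their required follow up period" leaves open which of the trial's two consents is meant.

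**Posted primary outcome.** SAP 7.5 gives Outcome Measure 1 the window "From the time of informed consent up to 2 years from the first dose of AST-VAC2". The table in SAP 7.5.1 has three overall rows (serious, non-serious, Grade 3 or higher) and three matching related rows. It has no pre-treatment row, and neither section limits the count to events starting after vaccination.

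**CSR.** SAP 5.7 separates pre-treatment AEs from TEAEs with an eCRF tick-box. SAP 6.2 lists them as separate CSR tables (14.3.3 and 14.3.4), beside an all-AE table (14.3.2).

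**End of the reporting window.** For the CSR, SAP 5.14.4 says "All patient visits occurring on or before this date will be analysed and summarised in the clinical study report including safety data to date", where the date is one cut-off for the whole trial. The posted window stops two years after first dose. SAP 7 says of the posted results: "The data presented will be consistent with the final CSR".

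**The concern.** Safety is the primary endpoint, and Outcome Measure 1 is how it will be read by anyone who sees only the public posting. An event that starts before the first dose cannot be an effect of AST-VAC2, yet it adds to the overall rows. With up to eight patients, a few screening-period events in people with advanced lung cancer would visibly change those counts. SAP 7 keeps the ClinicalTrials.gov tables out of the CSR, so the CSR's separate tables do not help a reader of the posting.

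The disagreement over consent makes the size of this contribution depend on site practice. A site following 7.1.2 records every event from HLA consent; a site following 9.3.2 and 9.3.3 records far fewer before main consent. At the other end, a late related event in a long-surviving early patient could be in the CSR but outside the posted window.

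**Working it through.** The plan states no figure on this point, so there is none to reproduce. The check compares the passages and then sets out the day arithmetic.

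**1. Do pre-vaccination events enter?** Outcome Measure 1 starts at consent and consent precedes dosing. No TEAE condition is stated, so they enter the overall rows. This holds whichever consent is meant.

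**2. Do they enter the related rows?** They should not. Possible, probable and highly probable in Protocol 9.2.4 each require onset in a time related to administration.

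**3. Whose events?** The measure uses the Safety Population (SAP 4.1: at least one vaccination). Patients who were only HLA-screened contribute nothing.

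**4. All-cause window after first dose.** Protocol 9.3.3 starts collection "by signing the main trial consent form and will continue until 30 days after the last vaccination"; after that only related AEs are collected. Six weekly vaccinations give five intervals:
- 5 × 7 + 30 = 65 days
- shortest, with 6-day intervals and the End of Vaccination visit at 25 days: 5 × 6 + 25 = 55
- longest, with 8-day intervals and the visit at 35 days: 5 × 8 + 35 = 75

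So all-cause events are collected for about 65/730 = 9% of the two-year label, which is why a few pre-dose weeks weigh heavily. Dose delays would lengthen the window.

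**5. Pre-dose share of background events.** Assuming a constant background rate, share = d / (d + window), where d is days from the start of collection to first dose. The documents do not give d. Protocol 7.1.2 sets a 28-day baseline period but lets main consent be earlier, and the notes to the schedule of events (Protocol 7.5) let HLA testing fall outside it. Both values of d are therefore assumptions.

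| d (days) | 65-day window | 75-day window | 55-day window |
|---|---|---|---|
| 28 | 28/93 = 30% | 28/103 = 27% | 28/83 = 34% |
| 60 | 60/125 = 48% | 60/135 = 44% | 60/115 = 52% |

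**6. Share of all events.** Suppose, as an assumption, that vaccine-related events over the 65 days equal background events. The post-dose part doubles to 130, and the shares become 28/158 = 18% and 60/190 = 32%.

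**7. Counts.** Assuming eight patients and one background AE per patient-month (30.4 days), 28 pre-dose days give 8 × 28/30.4 = 7.4 events against 8 × 65/30.4 = 17.1 afterwards. At half that rate the figures are 3.7 and 8.6; at double, 14.7 and 34.2. If HLA consent were at 60 days and main consent at 28, following 7.1.2 would add 8 × 32/30.4 = 8.4 events at the middle rate.

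**8. End of window.** Protocol 5.3 requires four vaccinations in patient 1 before patients 2 and 3 are recruited, and four in those two before the rest. The fourth patient's first dose is thus at least 3 × 7 + 3 × 7 = 42 days (36 to 48 with visit windows) after the first patient's. Quarterly calls after two years still collect new related AEs (Protocol 7.4.4). A gap between an early patient's two-year point and the cut-off is therefore possible. It affects totals only if that patient is still followed and a related AE is recorded in it.

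**The case against.** The strongest reply is that the CSR already handles this. Its all-AE table is labelled as such, pre-treatment events and TEAEs have their own tables, and the overview and grade tables (SAP Tables 9 to 11) use TEAEs. The related rows of the posted measure, which carry the causality part of the endpoint, should be clean. All of this stands. It confines the problem to the overall rows of the posted measure.

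A reader might infer that the conflict over consent is what brings pre-vaccination events in. The documents do not support that: the measure starts at consent, so these events would enter even if Protocol 7.1.2 and 9.3.3 agreed. The conflict changes only how many, and 7.1.2 itself refers to 9.3.

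A reader might also infer that the CSR and posted totals cannot agree. That too goes beyond the text. SAP 7 promises consistency in a different format, not identical tables. SAP 7.4 ties the two-year window to the interim report, which is also when the CSR is written, and provides for updating the posting if information changes by end of trial. No passage explicitly tells the programmers to drop events after two years. The totals may differ; they need not.

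Finally, the trial is descriptive and no test or interval depends on these counts.

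**Conclusion.** The point holds for the overall rows of Outcome Measure 1: as written, they include events from before the first vaccination. Separately, Protocol 7.1.2 contradicts 9.3.2 and 9.3.3 on what is collected between HLA consent and main consent.

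The size depends on unstated intervals. With a constant background rate and about 65 days of all-cause follow-up, pre-dose time holds about 30% of background events for an assumed 28 days and about 48% for an assumed 60. The 60-day figure applies all-cause collection over the whole 60 days, so if main consent came later it requires a site to follow 7.1.2. Neither figure is a share of all AEs, since vaccine-related events lower both.

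The differing end of window is a minor matter of labelling. Overall this is a moderate to small reporting defect, worth correcting because it touches the primary outcome and the remedy already exists in the SAP.

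**What to change.** 1. In SAP 7.5 and 7.5.1, restrict Outcome Measure 1 to TEAEs using the SAP 5.7 flag, or keep the consent start and give pre-treatment events their own row. If the first option is taken, footnote that the AE module in SAP 7.4 still starts at consent.
2. Reconcile Protocol 7.1.2 with 9.3.2 and 9.3.3, and name the consent that starts AE collection there, in Protocol 13.4 and in SAP 7.4 and 7.5.
3. State one end-of-window rule for the CSR and posted tables, or keep the two-year window and footnote any related AE recorded after it and before the cut-off. The footnote avoids unequal follow-up between patients, which a common cut-off would bring.

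The cost is minor SAP and protocol wording, a little programming with an existing flag, and, under the TEAE option, a small change to the stated time frame of the posted measure.

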### 7.1.3 Evaluations within 7 days of study enrolment

The following must be performed **within 7 days before** study enrolment:

- Female patients able to have children must have a negative result on a human chorionic gonadotropin (HCG) pregnancy test (serum or urine test is acceptable).
- Complete physical examination;
- Height, weight, WHO PS,
- Vital signs (temperature, seated BP and pulse rate);
- ECG;
- Laboratory tests (blood/urine samples). Laboratory tests relating to specific eligibility criteria must be performed to confirm a patient's eligibility prior to study enrolment:
  - Haematology – haemoglobin (Hb), white blood cells (WBC) with differential count (neutrophils, lymphocytes, platelets and eosinophils).
  - Biochemistry – sodium, potassium, adjusted calcium, phosphate, urea, creatinine, total protein, albumin, bilirubin, alkaline phosphatase (ALP) and alanine aminotransferase (ALT) or aspartate aminotransferase (AST) and C-reactive protein (CRP).
  - CEA sample
  - Urinalysis – pH, glucose, protein and blood.
  - Baseline research bloods (Please see [Section 8.0](#))

Investigators must enrol the patient on the trial once confirmed as eligible (see [Section 4.2](#)) and prior to the patient's first AST-VAC2 vaccination.

## 7.2 Evaluations during the trial

### Day of vaccination

- Symptom-directed physical examination: if clinically indicated, a symptom-directed physical examination is to be performed on the day of each vaccination before AST-VAC2 administration.
- WHO PS on the day of each vaccination.
- Vital signs, temperature, seated BP, pulse rate: must be assessed within 15 mins before the vaccination and within 15 mins after the vaccination.
- Adverse events and concomitant medications: At each visit, before each AST-VAC2 vaccination, an assessment of any AE experienced since the previous visit must be made by the Investigator, Research Nurse or suitably qualified member of the Investigator's team.

The start and stop dates of the AE together with the relationship of the event to AST-VAC2 must be recorded in the medical records.

All AEs must be graded according to NCI CTCAE Version 4.02 and protocol specific ISR grading system (See [Section 9.0](#) for further details regarding AE reporting requirements and ISR grading system).

Any concomitant treatment must be recorded in the medical records. (See [Section 9.0](#) for further details regarding AE reporting requirements.)

- COVID-19 vaccines: If a patient is administered a COVID-19 vaccination during the AST-VAC2 vaccination period, there should be an interval of 48 hours between the administration of the vaccines and they should be administered to different sites. The COVID-19 vaccine should be documented in the eCRF as a concomitant medication and any AEs should be assessed for causality to AST-VAC2 and the COVID-19 vaccination.
- Laboratory tests:  
Haematology and biochemistry:

**Week 1 vaccination**: laboratory tests must be repeated and reported prior to the first vaccination if the results used for enrolment purposes are >7 days prior to the day of vaccination.

